3.4 Primary Endpoint

3.4.1 Feasibility will be defined as: % approached, retention rate (% of consented patients who completed the intervention); % intended data collection, safety (# of adverse events).

3.4.2 Adherence will be monitored by electronic tracking from OT and PT notes and by self-report during the intervention.

3.5 Exploratory Outcomes

[REDACTED]

[REDACTED]

4.0 PATIENT ELIGIBILITY

Eligible patients are those who have been diagnosed with AML and will receive HMA or low-dose cytarabine+ Venetoclax.

4.1 Inclusion Criteria

1. ≥ 60 years of age

2. Diagnosis of AML
3. Plan to receive HMA or low-dose cytarabine + Venetoclax
4. Have caregiver(s) willing to participate

4.2 Exclusion Criteria

[figure not shown]
1. Patients receiving hospice care
2. Patients will be excluded if they are unable to participate per their oncology provider

5.0 STUDY PLAN

5.1 Patient Identification and Consent /Study Schema

Potentially eligible patients will be identified through pre-screening the Electronic Health Record after referring by oncologists or pharmacists. Eligible patients will be approached to confirm eligibility (which includes requesting permission of the patient's attending physician). The study coordinator will provide information about the study and invite participation. Seven days prior to and within three days after initiation 1st cycle HMA or low-dose cytarabine + VENE, written informed consent will be obtained from those eligible and interested in participating. If applicable, reasons for declining participation in the study will be recorded.

Study Schema

Recruitment of Patients

Approximately 100-150 patients with acute leukemia are admitted to UNC for treatment annually. We aim to enroll 20 patients (10 control and 10 intervention) with AML over 2 years. Given that recruitment to a pilot cluster randomized feasibility and acceptability trial may be lower than for an observational study, we project achieving our target sample within this timeframe.

Potentially eligible patients (diagnosis with AML) will be approached for enrollment by the study coordinator. Oncologists and nurse navigators will be provided a recruitment flier for the

study containing the purpose, a brief explanation of study protocols, and research team members' information. If the patient expresses interest in participating, the physician or pharmacist will relay this information to a research team member, who will provide more information about criteria for participation and a brief explanation of the study. Eligible patients will have up to 7 days before and within 3 days after initiation of chemotherapy to enroll in the study, and, if applicable, reasons for declining participation in the study will be recorded.

The first 10 patients will be assigned to the control group. All patients (assigned to either intervention or control groups) will undergo the exact same battery of quality of life, symptom, and functional measures at baseline (prior to beginning the intervention), and throughout different time points throughout the study (see Data Collection Procedures/timeline below). Once consent is provided, study personnel may contact enrolled participants up to 2 years from their acute leukemia diagnosis. All patients cluster randomized into the intervention group will receive standard care plus the PACT intervention for the duration of the study.

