2.0 STUDY PURPOSE AND DESIGN

This is a single institution, feasibility trial of 20 (10 control and 10 intervention) patients with the primary objective of assessing feasibility, acceptability, and change in pre and post measures of symptoms, function, and QOL by administering the PACT intervention.

Study subjects will be identified by the Study Coordinator through pre-screening through the electronic health record after being referred by the oncologists and pharmacists. Eligible patients will be approached by the Study Coordinator to confirm eligibility, which includes requesting permission of the patient's attending physician. Seven days prior to and within three days after initiation 1st cycle HMA or low-dose cytarabine + VENE, written informed consent will be obtained (A total of 10 days of recruitment period and baseline assessment).

First, ten participants in the control group will receive usual care. After the control patients have completed the study, then 10 intervention participants will receive the PACT intervention, a novel symptom management intervention, which aims to build patient skills to manage AML treatment-related, and chronic illness symptoms. Because patients receive chemotherapy during the first 7 days of hospitalization or clinic visit, the intervention will start at day 1 or day 2 of chemotherapy. During hospitalization, the PACT RN will assess AML symptoms daily (using PRO-CTCAE), and PACT OT and PT will assess function at baseline (day 1 or 2), days 3 or 4, and days 6 or 7. This study uses UNC hired staff of RNs, OTs, and PTs to deliver the intervention.

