10.2 Sample Size and Accrual

Sample size for this study is mainly determined by time and resource (budget) constraints. We will allocate 26 patients to the two groups (12 per group). We assume 20% of values will be missing or otherwise unusable, yielding complete data for 10 patients per group for analyses. As stated

above, estimation rather than statistical inference is our focus, and so it is not this project's goal to have adequate statistical power. We can focus instead on precision, and for the primary outcome of QOL (standardized), the half-width of a two-sided 95% confidence interval would be .9SD, assuming 10 patients per randomized group. We obtained this result using nQuery Advisor v7.0 software.

We claim such a study as feasible if and only if both (a) recruitment rate (p) is high enough and (b) retention rate (q) is sufficiently high, i.e., if both p and q are large enough. More specifically, this is to test the following hypothesis:

$$H_0: p \leq 50\% \text{ or } q \leq 50\% \text{ vs } H_1: p \geq 80\% \text{ and } q \geq 70\%.$$

Denote N as the number of eligible patients we try to recruit, and Y as the number of patients who are recruited, X as the number of patients (among the Y who are enrolled) who complete the PACT intervention. The target value of Y is 20, and we assume (1) N follows a negative binomial distribution, $NB(20, p)$, (2) X , conditional on ($Y = 20$), follows a binomial distribution $B(20, q)$. We further assume that N and X are independent. We list cut-offs and associated type I error and power under different N and X values for rejecting the hypothesis of $p \leq 50\%$ and the hypothesis of $q \leq 50\%$.

Recruitment (N: total number of patients being approached)

Y	Rejection Area	Type I error ($p \leq 50\%$)	Power ($p \geq 0.80$)
20	$N \leq 20+12$	0.108	0.994
20	$N \leq 20+13$	0.148	0.997
20	$N \leq 20+14$	0.196	0.999
20	$N \leq 20+15$	0.250	0.999

Retention (X: total number of patients who complete the intervention)

Y	Rejection Area	Type I error ($q \leq 50\%$)	Power ($q \geq 0.70$)
20	$X > 8$	0.748	0.995
20	$X > 9$	0.588	0.983
20	$X > 10$	0.412	0.952
20	$X > 11$	0.252	0.887

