Analyses will be conducted following an intention to treat approach, such that patients are analyzed as allocated. Descriptive statistics will be computed on all analysis variables at each time point separately for each condition. These values will be compared between the conditions at baseline to determine whether any imbalanced. These include means and standard deviations for continuous variables, and frequencies and percentages for categorical variables. As the primary analysis of pre and post values, we will fit an analysis of covariance (ANCOVA) model for each post outcome, with a main effect for group (intervention versus control) while controlling for the covariate of the corresponding baseline (pre) value. Sensitivity analyses will repeat this ANCOVA but adding demographic variables that are imbalanced at baseline, subject to sufficient sample size. This approach will allow us to assess whether the mean post values differ between groups for each measure through the regression coefficient for the main effect of group, as well as its 95% confidence interval. This information will be useful in planning for the subsequent R01, and we will calculate effect sizes for the post measure as the ratio of the mean difference between the intervention and the control groups to its standard deviation. For measures where more than one follow-up measure is collected, this approach can be extended through a linear mixed effects model approach to repeated measures analysis, and within-patient correlation can be estimated. If extensive (e.g., greater than 10%), multiple imputation will be considered for missing values. No formal significance testing will occur, as the intention is to evaluate and estimate effect sizes rather than formal hypothesis testing, and hence multiplicity is not a concern from this perspective.

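### Sections 5.1 and 10.2 call the groups randomised, but enrolment order assigns them, so PACT cannot be separated from calendar period, and 10.3 does not say so

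*Combined protocol and SAP*

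**What the plan says.** Three places describe the groups as randomised. Section 5.1 discusses "recruitment to a pilot cluster randomized feasibility and acceptability trial" and later says "All patients cluster randomized into the intervention group will receive standard care plus the PACT intervention". Section 10.2 derives its 0.9 SD half-width "assuming 10 patients per randomized group".

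The allocation rule itself is sequential. Section 2.0 says "This is a single institution, feasibility trial of 20 (10 control and 10 intervention) patients" and then "After the control patients have completed the study, then 10 intervention participants will receive the PACT intervention". Section 5.1 agrees: "The first 10 patients will be assigned to the control group".

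For the comparison of change, section 10.3 plans an ANCOVA of each post value on group and the matching baseline value. A sensitivity analysis adds demographic variables that turn out to be imbalanced. On baseline comparability it says "These values will be compared between the conditions at baseline to determine whether any imbalanced". The group coefficient, its 95% confidence interval and an effect size are offered as input to a later R01. Section 10.2 adds that "estimation rather than statistical inference is our focus".

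**The concern.** Randomisation is what would allow the group coefficient to be read as an effect of PACT. The labels in 5.1 and 10.2 claim that property, and the allocation rule does not provide it. The available text names no cluster unit, number of clusters, intracluster correlation or randomisation procedure. The Study Schema content is not shown, but assignment by enrolment order leaves nothing to randomise.

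Comparing change between groups is part of the primary objective in 3.1, and the effect size is meant to be carried forward. Someone planning the R01 who relies on 5.1 or 10.2 would have no warning that the estimate may include a difference between two periods in case mix, usual care, staff or data collection. Such a difference could inflate the apparent effect or hide a real one.

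**Working it through.** **1. The plan's own figure.** Section 10.2 gives a two-sided 95% half-width of 0.9 SD with 10 per group. Half-width = critical value × √(2/10), and √(2/10) = 0.447.
- Normal: 1.960 × 0.447 = 0.877 SD.
- t with 18 df: 2.101 × 0.447 = 0.940 SD.

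Both round to 0.9, so the arithmetic is sound. The figure covers sampling error only.

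**2. Aliasing.** Code group as 0 for controls and 1 for PACT, and period as 0 for the first cohort and 1 for the second. Under the rule in 2.0 and 5.1 the two columns are identical. The design matrix with intercept, baseline, group and period has 4 columns and rank 3, so a group effect and a period effect cannot both be estimated. Adding demographic covariates does not change this.

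**3. Separation in time.** Assume even accrual over the 2 years in 5.1, with a pause of g months while the last control finishes. Each cohort then enrols over (24 − g)/2 months, and the cohort midpoints lie (24 − g)/2 + g = (24 + g)/2 months apart.
- g = 3 (about day 90, Table 5): 13.5 months.
- g = 6 (section 5.4): 15 months.

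**4. Effect on the planned interval.** The documents give neither a drift b nor a pre-post correlation r, so both are assumed. The simulation used 10 per group, normal data with unit variances, a true PACT effect of 0, ANCOVA with 17 df and 400,000 replicates per cell. Two cases were run:
- Shift already in the baseline value and persisting: bias = b − r·b = b(1 − r).
- Drift acting after baseline: bias = b.

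Coverage of the nominal 95% interval:

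| Case | r | b = 0.1 | 0.2 | 0.3 | 0.5 | 0.8 SD |
|---|---|---|---|---|---|---|
| At baseline | 0.3 | 0.948 | 0.940 | 0.926 | 0.887 | 0.798 |
| At baseline | 0.5 | 0.949 | 0.944 | 0.936 | 0.911 | 0.856 |
| At baseline | 0.7 | 0.949 | 0.946 | 0.943 | 0.929 | 0.902 |
| After baseline | 0.3 | 0.945 | 0.929 | 0.901 | 0.810 | 0.594 |
| After baseline | 0.5 | 0.943 | 0.924 | 0.891 | 0.780 | 0.525 |
| After baseline | 0.7 | 0.941 | 0.911 | 0.862 | 0.700 | 0.368 |

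At b = 0 coverage is 0.950 in every cell. At r = 0.5 the bias left by a baseline shift is 0.05, 0.10, 0.15, 0.25 and 0.40 SD, and the mean half-width is 0.83 SD.

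**5. Would the planned baseline comparison reveal a shift?** The SE of the baseline difference is 0.447 SD and its 95% half-width 0.940 SD. With a true baseline shift of 0.3 SD:
- P(observed difference has the wrong sign) = Φ(−0.3/0.447) = 0.251.
- P(observed difference is at least 0.5 SD in absolute value) = 0.364, against 0.264 with no shift.

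The comparison can display a baseline shift, but only imprecisely. It carries no information about drift after baseline.

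**The case against.** The sequence is not hidden. Section 2.0 states it in full and 5.1 repeats it; 10.1 calls the study a pilot clinical trial, and 10.3 never uses the word randomised or claims an unconfounded estimate. The primary endpoint section (3.4) lists only feasibility and adherence, although 10.2 calls QOL the primary outcome. The aim is estimation, and 10.3 rules out formal testing. All of this is correct and limits the harm. It does not correct three labels that contradict the design, and an estimation aim removes error-rate claims but not bias.

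The drift sizes are assumptions, and the 0.83 SD half-width at r = 0.5 exceeds every one of them. The only mechanism the documents suggest is the forecast in 1.2 that lower-risk patients will move to community centres. It has no date or size and would act mainly through the baseline value, for which the ANCOVA partly adjusts. This stands: the figures show what drift could do, not that it will occur.

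Aliasing is exact for period as a two-level factor. A linear enrolment-order term could be fitted: with 20 equally spaced patients its correlation with group is 0.87, and the variance inflation is 1/(1 − 0.867²), about 4.0. But the cohorts do not overlap in time, so that adjustment would rest on extrapolation.

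Treatment, blood results and remission status are also recorded during follow-up, so some changes in background care may be visible. That would help interpretation without removing the confounding, and 10.3 does not plan that use.

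**Conclusion.** The concern holds. The documents attribute randomisation to a design that assigns by enrolment order, and 10.3 does not state the consequence: the group coefficient, its interval and the effect size estimate the PACT effect plus any period difference. That part rests on the text and needs no assumption about drift.

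The size of any bias cannot be derived from the documents. At r = 0.5, shifts up to 0.2 SD leave coverage near nominal (92% or better). Drift after baseline of 0.5 SD lowers it to about 78%, and of 0.8 SD to about 52%. Shifts already present at baseline do less harm: about 91% and 86% at the same sizes. These figures assume normal data, equal variances, 10 complete patients per group and the stated b and r.

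The recruitment and retention rule in 10.2 does not use this contrast and is unaffected. The point should be corrected because it changes what the comparison in the primary objective, and the effect size passed to the R01, can be said to show.

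**What to change.** Correct the three labels:
- 5.1, recruitment paragraph: *a pilot feasibility and acceptability trial with sequential, non-randomised control and intervention cohorts*.
- 5.1, assignment paragraph: *All patients assigned to the intervention cohort*.
- 10.2, precision statement: *10 patients per cohort*.

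Add to 10.3: *Because the cohorts are sequential, the group coefficient, its confidence interval and the effect size estimate the PACT effect plus any period or case-mix difference, and will not be used in R01 planning as an unconfounded PACT effect.*

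No planned analysis changes, and no new data, staff or patients are needed. The cost is a written amendment with IRB approval under 11.6, and a weaker claim for the group contrast.

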5.2 Study Assessments

At the time of baseline assessment, patients with no contraindications to activity will undergo quality of life, symptom, OT and PT assessments, as well as medical chart abstraction.

At follow up time points, participants will complete the assessments and questionnaires per the Time and Events table (see section 8.0). We have completed daily and weekly measures with adults undergoing a hematopoietic transplant^{26,27} and those with acute leukemia during their hospitalization.^{28,29} Patients are able to complete daily assessments within 5 minutes.

5.3 Description of Assessments and Questionnaires

Assessment Tool	Discipline	Indication
European Organization for Research and Treatment of Cancer QLQ-C30	PI or Research Assistant	Self-report QOL: functional scale & symptom scale
PRO version of the Common Terminology for Adverse Events (PRO-CTCAE)	PI or PACT RN	19 items** (diarrhea, chills, heartburn, nausea, appetite, mouth sores, vomiting, constipation, cough, rash, shortness of breath, fatigue, anxiety, sadness, nothing will cheer me up, pain, insomnia, concentration, and memory)
Activity Measure in Post-Acute Care (AM-PAC)	OT & PT	Guides discharge planning; guides resource utilization; provides insight re: patient mobility
Karnofsky Performance Scale (KPS)	PI or Research Assistant	Classified participants' functional impairment
Possibilities for activity Scale (PACTS)	PI or Research Assistant	Assessing self-efficacy and motivation of performing meaningful activity

Timed Up and Go~10 feet (3 meters)	PT	Assesses patient mobility, balance and fall risk
BERG Balance	PT	Falls Risk
Muscle Strength	OT	Prognostic & Predictive Marker, Handheld Dynamometry
Modified Canadian Occupational Performance Measure (COPM)	OT	Self-care, leisure, and productivity outcomes; goal attainment scale
Performance Assessment of Self-care Skills (PASS)	OT	Ability to perform daily tasks
Clock Drawing	OT	Assess cognitive abilities
Demographics and Clinical Characteristics	PI or Research Assistant	Demographic: date of birth/age, sex, race/ethnicity, insurance, education, income, marital/partner status, number of people in the household, employment status, insurance type, falls in last 6 months Clinical: type of acute leukemia, white blood cell, hemoglobin, hematocrit, platelets, lactate dehydrogenase, neutrophil count, cytogenetics and blast percentage, height and weight, comorbidity, and treatment type(s)
Care Transitions Measure (CTM)	PI or Research Assistant	Assesses readiness for discharge
Patient Activation Measure (PAM)	PI or Research Assistant	Assesses self-management
Preparedness for Caregiving Scale FACT-Leu Additional Concern subscale	PI or Research Assistant PI or Research Assistant	Assesses preparedness for caregiving Assess disease burden

5.3.1 QOL Assessment

Quality of life

The European Organization for Research and Treatment of Cancer QLQ-C30, widely used to assess QOL in patients with cancer, has 30 questions, grouped and scored to obtain both multi-item scales and single-item measures. It includes five functional scales, three symptom scales, one global health status/QOL scale and six symptom items. Functional scales are cognitive, emotional, physical, role, and social. Symptom scales are fatigue, nausea/vomiting, and pain; a global health status/QOL scale and 5 single items assess additional symptoms appetite loss, constipation, diarrhea, dyspnea, sleep disturbance, and perceived financial impact.

Scores of scales and single-item measures range from 0-100; higher scores indicate better QOL. Conversely, in symptom scales and symptom items, higher scores represent worse QOL.³⁰ We will use the PRO version of the Common Terminology for Adverse Events (PRO-CTCAE)³¹ to provide a detailed view of daily treatment-related symptoms and how they fluctuate.

5.3.2 PRO-CTCAE (daily measures)

This 78-item measure, developed at the National Cancer Institute (NCI) allows patients to self-report symptom-based adverse events. We will use a subset of 19 symptoms to assess symptom attributes (e.g., presence, frequency, severity, interference with symptom) deemed relevant for cancer patients; these symptom-items have been extensively evaluated by cancer patients using cognitive interview³² methods and found to be clear, comprehensible, and capable of measuring the symptoms of interest and are most relevant for this population, such as nausea and vomiting. In our bone marrow transplant study (preliminary study 3, in which most of the patients had some type of leukemia, these items captured symptoms of fatigue, diarrhea, heartburn, nausea, appetite, anxiety, mouth sores, vomiting, pain, constipation, sadness, cheering-up, insomnia, cough, rash, and shortness of breath. In the proposed study, both the control and intervention groups will be asked to answer the 19 questions daily to capture changes over time. Recent data have shown that daily collection of patient-reported symptoms is feasible and acceptable to bone marrow transplant patients in the inpatient setting, who are often patients with AML.³³ We will calculate a total symptom score. This symptom score represents treatment-related symptom burden for that patient on that particular day.

5.3.3 Functional Assessments

The following assessments will consist of the physical performance evaluation: Rate of Perceived Exertion, Activity Measure in Post-Acute Care, Clinician rated Karnofsky Performance Scale (KPS), Possibilities for Activity Scale (PACTS)³⁴(activity self-efficacy and expectations, related to engagement in meaningful activity), Timed Up and Go, muscle strength using hand dynamometer, BERG balance, Performance Assessment of Self-care Skills (PASS), clock drawing, and Canadian Occupational Performance Measure (COPM).

Role	Assessments
OT	PASS- Performance Rate Assessment of Self-Care Skills, Hand grip strength, Activity Measure for Post-Acute Care (AM-PAC) “6 clicks” - 6 items for OT, clock drawing
PT	Berg balance test, Timed Up and Go, Activity Measure for Post-Acute Care (AM-PAC) “6 clicks” - 6 items for OT; 6 items for PT; $\alpha = .92 - .94$

AM-PAC: OT and PT clinicians will objectively measure function using the activity Measure in Post-Acute Care (AM-PAC) “6 clicks.” The AM-PAC “6 clicks” is a valid tool for assessing function in patients receiving post-acute care.³⁵ The tool includes three domains: basic mobility function, and another form assesses daily activity function. Each item scores from 1 to 4, the lower the score, the lower the function. Due to the clinic environment consideration, we will only assess 5 items in the PT components (excluding “climbing 3-5 steps with a railing”).

Karnofsky Performance Scale (KPS) clinician-rated: The KPS index allows patients to be

classified as to their functional impairment. This can be used to compare effectiveness of different therapies and to assess the prognosis in individual patients. The lower the Karnofsky score, the worse the survival for most serious illnesses. We will use the clinician rated KPS.^{36,37}

Possibilities for activity Scale (PACTS)³⁴ measures the meaningful activity participants participated in. The scale includes two subdomains: activity self-efficacy and activity expectations.³⁴ Each item is scored in a Likert-type format ranging from 1 corresponds with “very little” to 5 represents “quite a lot”. The total score ranges from 12 to 60 with higher scores indicating that participants had higher self-efficacy and expectation on participating in meaningful activity.³⁴

Timed Up and Go: The Timed Up and Go is a performance test of physical mobility, and measures how long it takes the patient, in seconds, to stand up from a standard arm chair, walk a distance of approximately 10 feet, turn, walk back to the chair, and sit down again (Vincent et al, 2010).

BERG balance scale³⁸ is a 14-item scale used to measure balance of the older adult in clinical setting. Participants will be asked to perform their balance ability following the instructions, such as standing to sitting or standing on one foot. These tasks are common movement in daily life.³⁸ Each item is scored from 0 to 4, the higher the score, the higher the level of function.

Muscle Strength: Maximal muscle strength of the forearm flexor muscles will be measured using portable dynamometers (NexGen Ergonomics, Quebec, Canada). Maximal muscle strength of the forearm flexors will be performed in a standing position with each forearm flexed at 90 degrees. With the hand in a neutral (handshake) position, the participant will be instructed to inhale. Then, during the exhale, maximally grip the dynamometer for 3- 5 seconds while straightening the forearm longitudinally to the body.

Canadian Occupational Performance Measure (COPM)³⁹, administered by OT, is a tool to identify, prioritize, and evaluate patient’s perception of performing daily activity. Based on this tool, OTs will be able to identify prioritizing occupational task and develop goals for participants in the intervention group.

Performance Assessment of Self-care Skills (PASS)⁴⁰, administered by OT, is a tool to assess function. There are several components in the PASS. In our study, we will only use the medication management component, which will assess independence, safety, and adequacy. Additionally, based on the oral hygiene and toileting management components, our OT team develop washing hands component.

Clock Drawing, administered by OT, is a tool to assess cognition. This assessment tool has been identified to be a reliable tool to screen dementia and cognitive impairment, which is easily administered.⁴¹

Demographic and Clinical Characteristics: We plan to use National Institutes of Nursing Research (NINR) demographic common data elements: date of birth/age, sex, race/ethnicity, insurance, education, income, marital/partner status, number of people in the household,

employment status, insurance type, falls in last 6 months. We will obtain clinical data on type and amount of prior cancer treatment, medical comorbidities and medications, type/dose/date of AML treatment, days hospitalized during cancer treatment (including outside hospitalization if directly transferred to UNC from another facility), subsequent hospitalizations, date of death (if appropriate), electronic notes of occupational and physical therapy, blood test results (such as white blood cell count, Absolute neutrophil count, hemoglobin, platelet, lactate dehydrogenase, C-Reactive Protein), and remission status.

FACT-Leu additional concern subscale is a 17-item questionnaire. Each item is assessed by 0 to 4, the higher the score, the better the QOL.

